7.3 PATIENT RELATED OUTCOMES

7.3.1 Dermatology Life Quality Index (DLQI) questionnaire

At Baseline and at last visit, subjects will answer the 10-item DLQI questionnaire (see section 13.1), a validated quality-of-life questionnaire specific to dermatological conditions. The investigator or delegate will then check all questions of the questionnaire for completeness prior to the subject leaving the study visit.

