5.5 CLINICAL TRIAL VISIT DESCRIPTION AND PROCEDURES

5.5.1 Visit 1 – Screening/Baseline visit

- 1. Explain the nature and the constraints of the clinical trial to the subject and to parent.
- 2. Have the subject read, understand, date and sign an approved informed consent form (ICF). Give a dated and signed copy to each subject and parent/guardian if applicable.
- 3. If subject female of childbearing potential agrees to participate to the clinical trial, make sure she is using the required method(s) of contraception (see inclusion criteria 4.2.1). Make sure that the urine pregnancy test is done and the result is negative before subject inclusion in the trial
- 4. Log into the electronic case report form (eCRF) to get a Subject Identification Number.
- 5. Question the subject about demography, medical history (including flushing and rosacea co-morbidities), prior and concomitant therapies (including rosacea last treatment).

b. Photography consent and standardized photography + facial redness colorimetric measurements at selected centers only.

c. AEs are to be collected starting from the signing of the Informed Consent Form.

d. Assessments to be performed in case of early termination visit.

Protocol N° RD.03.SPR.113322

version Final dated 10-FEB-2017

Page 44 of 106 CONFIDENTIAL

- 6. Inform the subject about authorized and prohibited concomitant therapies. If the subject requires a medication washout period, the subject's baseline evaluation must be conducted after the washout period has been completed.
- Check inclusion/exclusion criteria (see sections 4.2.1 and 4.2.2).
- 8. Conduct facial inflammatory lesion count (see section 7.1.1).
- 9. Assess and record the severity of the diffused facial erythema of rosacea using CEA (see section 7.1.2).
- 10. Perform and record Investigator's Global Assessment (IGA) (see section 7.1.3).
- 11. Evaluate and record the severity of subject's facial stinging/burning sensation (see section 7.1.4).
- 12. Assess and record the severity of the Ocular signs and symptoms (see section 7.1.5).
- 13. Record in medical history the frequency of flushing (average per week) and the severity as reported by subject for the last week before baseline visit (see section 7.1.6).
- 14. Ask subject to complete the Dermatology Life Quality Index (DLQI) questionnaire (see 13.1) and review for completion;
- 15. Ask subject to complete the EQ-5D-5L questionnaire (see 13.2) and review for completion;

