5.5.3 Visit 4- Week 12 / Last clinical trial visit

- Question the subject and record the occurrence of any new adverse events and/or any changes to adverse events that were ongoing at the previous clinical trial visit. Document all changes in the CRF.
- 2. Enquire whether any concomitant therapies have been added, stopped, or changed since the subject's last visit. Document all changes in the CRF.
- 3. Conduct facial inflammatory lesion count (see section 7.1.1).
- 4. Assess and record the severity of the diffused facial erythema of rosacea using CEA (see section 7.1.2).
- 5. Perform and record Investigator's Global Assessment (IGA) (see section 7.1.3).

Protocol N° RD.03.SPR.113322

version Final dated 10-FEB-2017

Page 47 of 106 CONFIDENTIAL

- 6. Evaluate and record the severity of subject's facial stinging/burning sensation (see section 7.1.4).
- 7. Assess and record the severity of the Ocular signs and symptoms (see section 7.1.5).
- 8. Check subject's diary and record the frequency of flushing for each week as reported by subject in the diary (see section 7.1.6).
- 9. Ask the subject to assess her/his Global Improvement in Rosacea (see section 7.1.7) and record the outcome:
- 10. Ask subject to complete the Dermatology Life Quality Index (DLQI) questionnaire (see 13.1) and review for completion;
- 11. Ask subject to complete the EQ-5D-5L questionnaire (see 13.2) and review for completion;
- 12. Ask subject to complete the WPAI:GH questionnaire (see 13.3) and review for completion;
- 13. Ask subject to complete the Subject Satisfaction questionnaire (see 13.4) and review for completion;
- 14. Perform a urine pregnancy test (UPT) for female subjects of childbearing potential.
- 15. For selected sites only, take photographs of the face according to the provided photographic procedure, only if subject has agreed on the approved ICF.
- 16. For selected sites only, perform facial redness colorimetric measurements.
- 17. Complete the Exit form in the CRF and give the reason for clinical trial discontinuation.
- 18. Investigational product dispenser will:
 - a) Check the investigational products; review the subject's diary for completion and accuracy interview the subject about compliance. All missing tubes must be documented on the eCRF comments section and on other accountability forms.
 - b) Record the investigational products and Facial Moisturizer compliance on the eCRF.

Protocol N° RD.03.SPR.113322

version Final dated 10-FEB-2017

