7.1.2 Clinician's Erythema Assessment (CEA)

The evaluator will assess the subject's diffuse persistent facial erythema of rosacea by performing a static ("snap shot") evaluation of erythema severity, at a social distance of approximately 50 cm, using CEA at each visit. The evaluator should make no reference to previous assessments when evaluating the subject's erythema of rosacea and CEA must be evaluated after the inflammatory lesion count.

Protocol N° RD.03.SPR.113322

version Final dated 10-FEB-2017

Page 57 of 106 CONFIDENTIAL

Grade	Description
0	Clear skin with no signs of erythema
1	Almost clear; slight redness
2	Mild erythema; definite redness
3	Moderate erythema; marked redness
4	Severe erythema; fiery redness

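### The visit steps list every subject-completed instrument after the evaluator's count and gradings, and nothing in the plan requires self-reports first, so the evaluator's findings could colour the patient-reported outcomes

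*Protocol*

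**What the plan says.** Protocol 5.5.3 (Week 12 / last visit) numbers its steps. The first is the adverse-event interview: "Question the subject and record the occurrence of any new adverse events and/or any changes to adverse events". Concomitant therapies are step 2, the lesion count step 3, CEA step 4, IGA step 5, stinging/burning step 6, ocular grading step 7 and the flushing diary check step 8. Step 9 is the first self-assessment: "Ask the subject to assess her/his Global Improvement in Rosacea (see section 7.1.7) and record the outcome". DLQI, EQ-5D-5L, WPAI:GH and the satisfaction questionnaire are steps 10 to 13. The end of 5.5.2 applies the last-visit procedures to early termination.

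Protocol 5.5.1 (Screening/Baseline) has the same pattern. The count, gradings and flushing history are steps 8 to 13. Step 14 then reads "Ask subject to complete the Dermatology Life Quality Index (DLQI) questionnaire (see 13.1) and review for completion", followed by EQ-5D-5L (15) and WPAI:GH (16).

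Sections 7.3.1 to 7.3.3 say nothing about timing relative to the evaluator's work. They require only that "The investigator or delegate will then check all questions of the questionnaire for completeness prior to the subject leaving the study visit". Section 7.3.4 on the satisfaction questionnaire sets no timing beyond the last visit.

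The protocol does fix an order elsewhere; section 7.1.2 says that "CEA must be evaluated after the inflammatory lesion count". The one limit on conversation, in 6.5.1, covers the investigational products and not the evaluator's findings.

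**The concern.** A patient-reported outcome is most useful when the answer is the subject's own. In the listed order the subject has been interviewed, counted and graded before answering anything, and the plan has no safeguard against a finding being mentioned on the way.

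Some items ask about what has just been examined. Satisfaction items 2 and 3 (protocol 13.4) concern improvement in facial lesions and redness. The global improvement scale (7.1.7) asks for an overall judgement on signs and symptoms directly after the evaluator's own global grading.

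These outcomes are tested. Global improvement is a secondary efficacy endpoint (protocol 9.1.1.2; SAP 4.1.2, Table 22). SAP 6.4 analyses the questionnaires in the same way as the primary endpoint, with p-values in Tables 31, 33 and 35 to 39, at the two-sided 0.05 level of SAP section 6.

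Blinding the evaluator does not settle the matter. If doxycycline lowers lesion counts, correct blinded findings differ by arm, and so would any remark based on them. Part of a difference in a self-report could then repeat the lesion count.

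**Working it through.** **Order of the steps**

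| Visit | Evaluator count and gradings | Subject-completed instruments | Listed after all gradings |
|---|---|---|---|
| Baseline (5.5.1) | count, CEA, IGA, stinging/burning, ocular: steps 8–12; flushing history: 13 | DLQI 14, EQ-5D-5L 15, WPAI:GH 16 | 3 of 3 |
| Week 12 / early termination (5.5.3) | count, CEA, IGA, stinging/burning, ocular: steps 3–7; diary check: 8 | global improvement 9, DLQI 10, EQ-5D-5L 11, WPAI:GH 12, satisfaction 13 | 5 of 5 |

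The flushing diary is filled in at home before the visit, so it falls outside the point.

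**The plan's own figure**

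Inputs (protocol 9.2): difference 15, SD 35, power 90%; two-sided 0.05 from SAP section 6.

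- n per group = 2 × [35 × (1.960 + 1.282) / 15]² = 114.4. The plan states 114, and power at 114 is 0.899.
- Enrolment: 114 / 0.85 = 134.1, so 135 per group, as stated.

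The sample size reproduces to within rounding. The point does not depend on it; only the ratio 15/35 = 0.43 SD and the group sizes are used below.

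**Illustration on assumed carry-over**

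The documents give no figure for carry-over. Assume that the evaluator's finding differs between arms by 15/35 SD, that the subject's own view does not differ at all and is uncorrelated with that finding, and that the answer takes up a fraction w of it.

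- Shift in SD units = w × (15/35) / √(1 + w²)
- Noncentrality δ = shift × √(n/2), with n per arm
- Probability of a significant result = P(Z > 1.96 − δ) + P(Z < −1.96 − δ)

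| w | Shift (SD) | δ, n = 135 | Significant | δ, n = 114 | Significant |
|---|---|---|---|---|---|
| 0.1 | 0.043 | 0.35 | 6.4% | 0.32 | 6.2% |
| 0.2 | 0.084 | 0.69 | 10.6% | 0.63 | 9.7% |
| 0.3 | 0.123 | 1.01 | 17.3% | 0.93 | 15.3% |

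Without carry-over the figure is 5%. Two group sizes are shown because missing questionnaire answers are not imputed (protocol 9.1.2.4; SAP 5.4). Subjects who leave early but attend a termination visit still contribute, so the number analysed probably lies between 114 and 135.

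**The case against.** **The list may be a checklist rather than a sequence.** No sentence declares it binding. Baseline step 7 checks eligibility before the count (8) and IGA (10) that eligibility needs. The rule on CEA in 7.1.2 repeats an order the list already shows, which suggests that order binds only where stated. Protocol 10.1 also promises a site manual that is not available here. This stands. It means the order is uncontrolled rather than mandated the wrong way; the gap remains.

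**No passage says that findings are shared.** This stands too: the carry-over is a possibility, not something the plan instructs.

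**The instruments differ.** DLQI asks about the past week, WPAI:GH about hours and impairment over seven days, and EQ-5D-5L about such things as walking and self-care. These are poor candidates to echo a lesion score. Accepted; the point rests mainly on global improvement and a few satisfaction items.

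**The illustration has no source for w.** It also sets the subject's own view to zero difference and zero correlation with the evaluator's finding, although subjects see their own faces. Accepted; it is a scale for thought, not an estimate.

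**Moving everything first would create a new problem.** Satisfaction item 6 asks about side effects, and 8.2.1 wants an open adverse-event question that does not steer the answer. This stands and shapes the fix.

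A reader might also infer that hearing a grade of severe at entry and of improved at the end inflates the fall in DLQI within each arm. The documents do not support that. No evaluator scale has a grade of improved: CEA and IGA are static scores made without reference to earlier assessments. Every subject must be IGA 4 at entry, so any effect of that grade at baseline is common to both arms, and the planned tests compare arms.

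**Conclusion.** The point holds as a modest design weakness. All three baseline instruments and all five at the last visit are listed after the evaluator's count and gradings, and nothing requires the reverse or limits what the evaluator says about findings. Answers could be influenced, most plausibly for global improvement and the satisfaction items on lesions and redness, less so for DLQI, EQ-5D-5L and WPAI:GH.

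The size is unknown. The 6% to 17% range (6% to 15% with 114 per arm) rests on an assumed uptake of 10% to 30%, an evaluator difference equal to the planned effect, and no true difference in the subject's own view. It should not be cited as a bias estimate.

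A reader might infer that the patient-reported results are biased in favour of the combination, or that the main result is in doubt. Neither follows. The carry-over is not documented, the evaluator is meant to be blind to treatment, and the primary endpoint and sample size are untouched. The documents contain no contradiction here; this is a cheap improvement worth making.

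**What to change.** - **5.5.1:** state that DLQI, EQ-5D-5L and WPAI:GH are self-completed after consent and before the lesion count and gradings. If a washout is needed, do this at the visit where baseline is evaluated.
- **5.5.3 and early termination:** state that global improvement, DLQI, EQ-5D-5L and WPAI:GH are self-completed before the lesion count and gradings. Place the satisfaction questionnaire after the open adverse-event question of 8.2.1, so that its side-effect item does not prime that question, but also before the count and gradings.
- **7.3.1 to 7.3.4:** have completeness checked by a delegate other than the evaluator. Sections 7.3.1 to 7.3.3 already allow a delegate. Section 7.3.4 needs the same wording, because the side-effect item sits in that questionnaire and the evaluator should not read it before scoring lesions.

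The cost is protocol and site-manual wording; no visit, assessment or change of sample size is needed. There are two small downsides. Some subjects who prove ineligible will have filled in three short questionnaires. DLQI item 1, which mentions stinging, will precede the stinging/burning score, though equally in both arms.

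If visits have already taken place, report the order actually used as a limitation on the patient-reported results.

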7.3.2 EQ-5D-5L questionnaire

Subjects will answer the quality of life questionnaire EQ-5D-5L at Baseline visit and at last visit. EQ-5D-5L is a 5-level, 5-dimensional format standardized instrument for use as a measure of health outcome. Applicable to a wide range of health conditions and treatments, it provides a simple descriptive profile and a single index value for health status. EQ-5D was originally

Protocol N° RD.03.SPR.113322

version Final dated 10-FEB-2017

Page 62 of 106 CONFIDENTIAL

designed to complement other instruments but is now increasingly used as a 'stand-alone' measure. EQ-5D-5L is designed for self-completion by respondents. It is cognitively simple; taking only a few minutes to complete (see section 13.2). The investigator or delegate will then check all questions of the questionnaire for completeness prior to the subject leaving the study visit.

7.3.3 Work Productivity and Activity Impairment Questionnaire: General Health Problem (WPAI:GH) modified for Rosacea.

Subjects will answer the quality of life questionnaire WPAI: GH at Baseline visit and at last visit. The WPAI: GH questionnaire consists of six questions (see section 13.3). It is an instrument to measure impairments in both paid work and unpaid work. It measures absenteeism, presenteeism as well as the impairments in unpaid activity because of health problem during the past seven days. It has been validated to quantify work impairments for numerous diseases including dermatological diseases such as psoriasis^{1.16}. In addition, the WPAI: GH questionnaire has been used to compare work impairments between treatment groups in clinical studies or between subjects with different disease severity levels. As per WPAI questionnaire adaptation guidelines, the questionnaire has been adapted for rosacea by replacing the term 'your health problems' by 'your rosacea'.

The investigator or delegate will then check all questions of the questionnaire for completeness prior to the subject leaving the study visit.

7.3.4 Subject satisfaction questionnaire

At last visit, subjects will complete a questionnaire (see section 13.4).

7.4 OTHER ASSESSMENTS

7.4.1 Photography

Standardized photographs on the face (1 front view and 2 profile views) will be taken at selected investigational sites at each study visit. Pictures will be used for illustrative purpose and will not be subject to analysis.

7.4.2 Facial redness colorimetric measurements

Complementary facial redness colorimetric measurements will be performed using a Chromameter at selected investigational sites, depending on material availability.

Protocol N° RD.03.SPR.113322

version Final dated 10-FEB-2017

Page 63 of 106 CONFIDENTIAL

7.5 APPROPRIATENESS OF MEASUREMENTS

The clinical efficacy assessments will be based on inflammatory lesion counts, evaluation of facial erythema, stinging/burning sensation and flushing. The methods are established in the evaluation of rosacea products and used in previous studies with the study products.

Safety is documented by recording adverse events on an ongoing basis as a well-established process in clinical trials. In case of reporting of a worsening of rosacea, specific complementary data will be collected.

Impact of study treatments on subjects' quality of life will be measured by using specific questionnaires. DLQI and EQ-5D-5L are two validated questionnaires for evaluating quality-of-life: While EQ-5D-3L is more general and not disease-specific, the DLQI focuses on the impact of dermatological diseases on the quality-of-life.

The WPAI:GH questionnaire is a validated instrument to quantify work impairments for numerous diseases including dermatological conditions.

To collect specifically the patient satisfaction outcome, a subject satisfaction questionnaire will be used at the end of the study to collect the subjects' feedback on the treatment regimen, the level of satisfaction and future usage.

Protocol N° RD.03.SPR.113322

version Final dated 10-FEB-2017

Page 64 of 106 CONFIDENTIAL

8. ADVERSE EVENT

8.1 **DEFINITIONS**

8.1.1 Adverse Events (AE)

According to ICH E2A, an AE is any untoward medical occurrence in a subject or clinical investigation subject administered a pharmaceutical product and which does not necessarily have a causal relationship with this treatment. An AE can therefore be any unfavorable and unintended sign (including an abnormal laboratory value), symptom, or disease temporally associated with the use of a medicinal (investigational) product, whether or not related to the medicinal (investigational) product.

Thus any new sign, symptom or disease, or clinically significant increase in the intensity of an existing sign, symptom or disease since the first visit (including the disease being treated), should be considered as an adverse event. Lack of efficacy should not be considered as an AE.

Each new episode of a chronic disease (e.g., hay fever, allergy, etc.) from the screening visit should be reported as a new AE.

Notes:

- Any new sign or symptom reported by the subject that appears after accidental or intentional overdose or misuse should also be reported as an AE.
- There should be an attempt to report a diagnosis rather than the signs, symptoms or abnormal laboratory values associated with the report of an AE. However, a diagnosis should be reported only if, in the Investigator's judgment, it is relatively certain. Otherwise, symptoms, signs, or laboratory values should be used to describe the AE.
- Pregnancy should not be considered as an adverse event but must be followed up as described in section 8.3
- For an AE of irritation, the "date of onset" should be the date that the first symptom occurred.

8.1.2 Serious Adverse Events (SAE)

Protocol N° RD.03.SPR.113322

version Final dated 10-FEB-2017

Page 65 of 106 CONFIDENTIAL

A serious adverse event is any untoward medical occurrence that at any dose:

- results in death,
- · is life-threatening,
- requires hospitalization or prolongation of existing hospitalization,
- · results in persistent or significant disability/incapacity, or
- is a congenital anomaly/birth defect.

Important medical events that may not result in death, be life-threatening, or require hospitalization may be considered an SAE when, based upon appropriate medical judgment, they may jeopardize the safety of the subject, and may require medical or surgical intervention to prevent one of the outcomes listed in this definition. Examples of such events are intensive treatment in an emergency room or at home for allergic bronchospasm, blood dyscrasia, or convulsions that do not result in hospitalization.

Note:

- The term "life-threatening" refers to an event in which the subject was at risk of death at the time of the event; it does not refer to an event which hypothetically might have caused death if it was more severe.
- Inpatient hospitalization is considered to have occurred if the subject has had to stay in hospital overnight. The criterion for the prolongation of hospitalization is also defined as an extra night at the hospital. Hospitalization may not constitute sufficient grounds to be considered as an hospitalization if it is solely for the purpose of diagnostic tests, (even if related to an AE), elective hospitalization for an intervention which was already planned before subject enrolment in the clinical trial, admission to a day-care facility, social admission (e.g., if the subject has no place to sleep), or administrative admission (e.g., for a yearly examination).

8.1.3 Unexpected adverse drug reaction

According to ICH E6, an unexpected adverse drug reaction is defined as an adverse reaction, the nature or severity of which is not consistent with the applicable study drug information.

8.1.4 Adverse event reporting period

The clinical trial period during which AEs must be reported is the period from when the subject signs the Informed Consent Form to the end of the subject's participation.

The sponsor should be informed if the investigator becomes aware of any unusual safety information or any safety information that appears to be drug-related involving a subject who has

Protocol N° RD.03.SPR.113322

version Final dated 10-FEB-2017

Page 66 of 106 CONFIDENTIAL

participated in a clinical trial, even after a subject has completed the clinical trial. The investigator should be diligent in looking for possible latent safety effects that do not appear until a medication has been discontinued.

8.1.5 **Severity**

Severity is a clinical determination of the intensity of an AE and not of a disease.

The investigator will classify the intensity of AEs using the following definitions as a guideline for all AEs occurring during clinical trials conducted or sponsored by GALDERMA. For this classification, the investigator will take into account the possible range of the intensity of the event and report the grade of intensity which is the most appropriate according his medical judgment.

Mild Awareness of sign or symptom, but easily tolerated

Moderate Discomfort, enough to cause interference with usual activity

Severe Incapacitating with inability to work or perform usual activity

